8.4. Withdrawal Criteria/Study Discontinuation

Subjects may withdraw from the study at any time without stating a reason and without prejudice to further treatment. The Investigator may withdraw a subject from the study and discontinue study treatment and assessments at any time due to safety concerns. Full skin examination will be performed at each scheduled study center visit. If SD-101 causes any significant rash that has not occurred previously in the subject, the Investigator should consider discontinuing the subject. In addition, if lesions appear to significantly worsen above the normal cycle seen in the patient, with use of SD-101, the Investigator should consider discontinuing the subject.

Early discontinuation of any subject who has given informed consent / assent to participate will be recorded including the reason for discontinuation. The primary reason for a subject withdrawing prematurely will be selected from the following standard categories of early discontinuations.

1. Adverse Event (Adverse Reaction): Clinical events occurred that are reported that in the medical judgment of the Investigator are grounds for discontinuation in the best interests of the subject.
2. Withdrawal of Consent: The subject desired to withdraw from further participation in the study. The subject is not obligated to provide any reason for withdrawal of consent, but where a reason is given this will be recorded on the eCRF.
3. Protocol Violation: The subject failed to adhere to the protocol requirements, at the Investigator's discretion.

4. Lost to Follow-Up: The subject stopped coming for visits and study personnel were unable to contact the subject.
5. Other: The subject was terminated for a reason other than those listed above, such as, termination of study by Sponsor.

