9.3. Study Design

This is an open label extension, multi-center study to assess the continued safety of SD-101 cream (containing 6% allantoin) in treating subjects with Simplex, Recessive Dystrophic, and Junctional non-Herlitz Epidermolysis Bullosa.

SD-101 cream (containing 6% allantoin) will be applied topically, once a day to the entire body for the duration of the study. Subjects who successfully complete the SD-003 study will be eligible to roll over into the SD-004 study. The baseline visit 1 will occur at the final visit date for SD-003. The BSA assessment from the final SD-003 study will be used as the baseline information at visit 1 for the SD-004 study. The subject will return to the study site once every 3 months for visit 2 (14 days \pm 7 days from baseline) through visit 14 (1080 days \pm 7 days from baseline) to have BSA assessed. Body Surface Area will be assessed at all subsequent scheduled study center visits. Scheduled study center visits occur every 6 months after visit 14 (visits 16, 18, 20, etc.). After completion of visit 14, the next subject visit (visit 15) will be a phone call from the site to the patient. Telephone visits will occur every 6 months thereafter (visits 17, 19, 21, etc.) and include assessment of adverse events and concomitant medications only. At the Investigator's discretion, the subject may be asked to complete a study center visit in place of a phone call visit. If a study center visit is requested, no additional assessments (other than collection of information on adverse events and concomitant medications) will be required (see [Section 11](#) – Study Schedule for details).

All females of childbearing potential must have a negative urine pregnancy test prior to enrolling in the study and must agree to use some form of birth control or agree to remain abstinent until

the study is completed. Since a pregnancy test will be performed at the final visit for SD-003, the results from that test can be utilized for entry into the SD-004 study. In addition, a urine pregnancy test will be performed every 6 months and at the final visit.

Safety assessments will include monitoring of tolerability, adverse events, and physical examinations.

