11. STUDY SCHEDULE

Procedure Visit	1 Screening/ Baseline	2 Week 2	3 Month 3	4 Month 6	5 Month 9	6 Month 12	7, 9, 11, and 13 Months 15, 21, 27, and 33	8, 10, 12, and 14 Months 18, 24, 30, and 36	15 (odd visits) Month 39 Phone Call	16 (even visits) Month 42 Site Visit	Alternate Phone Call and Site Visit until Final Study Visit/Early Termination ^a	Final Study Visit/Early Termination
Study Day (± 7 Days)	0	14	90	180	270	360	450, 630, 810, and 990	540, 720, 900, and 1080	1170	1260	-	-
Informed consent / assent signed	X											
Inclusion/Exclusion assessment	X											
Demographic, medical and medication history	X								X	X		X
Physical examination ^b	X											X
Height, weight, and temperature	X											X
Assess BSA ^c	X	X	X	X	X	X	X	X		X		X
Urine pregnancy test (females only) ^d	X			X		X		X		X		X
Dispense/re-dispense SD-101 cream ^e	X	X	X	X	X	X	X	X		X		X
Collect SD-101 cream for the purpose of drug accountability		X	X	X	X	X	X	X		X		X
Collect all SD-101 cream												X

Procedure Visit	1 Screening/ Baseline	2 Week 2	3 Month 3	4 Month 6	5 Month 9	6 Month 12	7, 9, 11, and 13 Months 15, 21, 27, and 33	8, 10, 12, and 14 Months 18, 24, 30, and 36	15 (odd visits) Month 39 Phone Call	16 (even visits) Month 42 Site Visit	Alternate Phone Call and Site Visit until Final Study Visit/Early Termination^a	Final Study Visit/Early Termination
Monitor adverse events	X	X	X	X	X	X	X	X	X	X		X
Monitor use of concomitant medications	X	X	X	X	X	X	X	X	X	X		X

- a. After completion of visit 14, the subject will return to the site once every 6 months (visits 16, 18, 20, etc.), with the intermittent 3 month visits conducted via telephone (visits 15, 17, 19, etc.). Telephone visits will include assessment of adverse events and concomitant medications only. At the Investigator's discretion, the subject may be asked to complete a study center visit in place of a phone call visit. If a study center visit is requested, no additional assessments (other than collection of information on adverse events and concomitant medications) will be required.
- b. A complete physical examination will be performed at the final visit. The physical examination performed at the final visit for SD-003 will be utilized as the baseline assessment for SD-004.
- c. The BSA assessment will be performed at visits 2 through 14 and at all subsequent scheduled study center visits. The BSA assessment performed at the final visit for SD-003 will be utilized as the baseline assessment for SD-004.

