11.4. Definitions

Adverse Event (AE)

Any untoward medical occurrence in a patient, administered a medicinal product and which does not necessarily have to have a causal relationship with this treatment. An adverse event (AE) can therefore be any unfavorable and unintended sign (including an abnormal laboratory finding, for example), symptom, or disease temporally associated with the use of a medicinal product,

whether or not considered related to the medicinal product. AEs may include the onset of new illness and the exacerbation of pre-existing conditions.

The routine evolution of the disease condition under treatment according to the protocol will be evaluated as part of the disease symptoms assessments. Changes in the disease condition may not qualify as AEs. However, if there is a clinically relevant worsening of a sign or symptom of the condition under treatment and the outcome fulfills the definition of an AE, it must be reported as directed in the protocol.

Adverse Drug Reaction (ADR)

All events considered to be noxious and unintended responses to a medicinal product related to any dose should be considered adverse drug reactions, with the exception of skin site changes determined by the Investigator to be related to SD-101 dermal cream. These changes will be captured during the skin site evaluations (refer to [Section 9.3](#)). The phrase “responses to a medicinal product” means that a causal relationship between a medicinal product and an adverse event is at least a reasonable possibility, *i.e.*, the relationship cannot be ruled out.

Serious Adverse Event (SAE)

An adverse event that at any dose:

- Results in death
- Is life-threatening (*i.e.* the patient was at risk of death at the time of the event; it does not refer to an event which hypothetically might have caused death if it was more severe)
- Results in hospitalization or prolongation of existing hospitalization
- Results in persistent or significant disability/incapacity
- Is a congenital anomaly / birth defect
- Is considered to be an important medical event

Based upon medical and scientific judgment, important medical events that may not be immediately life-threatening, or result in death or hospitalization, but may jeopardize the patient or may require intervention to prevent one of the other outcomes listed in the definition above may be considered a serious adverse event.

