Hospitalizations are defined as initial or prolonged admissions that include an overnight stay. Hospitalization or prolonged hospitalization for technical, practical or social reasons, in the absence of an adverse event is not an SAE.

Pregnancy

Pregnancy itself is not considered an AE. Pregnancies will be reported and documented on a separate pregnancy report form provided to the sites. However, any pregnancy complication, spontaneous or elective abortion, still birth, neonatal death, or congenital anomaly will be recorded as an AE or SAE.

Unexpected Adverse Drug Reaction

An adverse reaction, the nature or severity of which is not consistent with applicable product information (*e.g.*, Investigator’s Brochure for an unapproved investigational medicinal product).

Suspected Unexpected Serious Adverse Reaction (SUSAR)

A SUSAR is a serious adverse event that is suspected to be related to the administered medicinal product and the nature or severity of which is not consistent with applicable product information.

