11.4.2. Adverse Event Reporting

The Investigator shall immediately report any serious adverse event that occurs to the Sponsor. Immediate reporting allows the Sponsor to take the appropriate measures to address potential new risks in a clinical trial. Therefore, the immediate report should be made by the Investigator within a very short period of time and under no circumstances should this exceed 24 hours following knowledge of the serious adverse event.

The Sponsor is required to expedite the reporting to all concerned Investigators / Institutions, to the IRBs, where required, and to the regulatory authorities of all adverse drug reactions (ADRs)

that are serious, unexpected and reasonably associated with the investigational product as assessed by the Sponsor. Such expedited reports should comply with the applicable regulatory requirements and with the ICH Guideline for Clinical Safety Data Management: Definitions and Standards for Expedited Reporting (E2A).

The Sponsor will submit to the regulatory authorities all safety updates and periodic reports, as required by applicable regulatory requirements.

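### The ADR definition excepts SD-101-related skin site changes without limit by seriousness, refers them to an evaluation the protocol does not describe, and conflicts with the SUSAR definition over expedited reporting

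*Protocol*

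**What the plan says.** Section 11.4 counts as an ADR any noxious, unintended response with at least a possible causal link to the product, "with the exception of skin site changes determined by the Investigator to be related to SD-101 dermal cream". It continues: "These changes will be captured during the skin site evaluations", with a reference to Section 9.3. Neither sentence mentions seriousness or severity.

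On safety, Section 9.3 says: "Safety assessments will include monitoring of tolerability, adverse events, and physical examinations". Section 11.2 specifies that tolerability means tolerability at the application sites, and refers to the Section 11 schedule for timing. Section 8.4, on withdrawal, adds: "Full skin examination will be performed at each scheduled study center visit". Footnote b of the schedule says: "A complete physical examination will be performed at the final visit"; the baseline examination is taken from the final SD-003 visit.

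On reporting, Section 11.4 says: "A SUSAR is a serious adverse event that is suspected to be related to the administered medicinal product", with the further condition that it is unexpected. Section 11.4.2 sets the Sponsor's expedited duty in terms of ADRs "that are serious, unexpected and reasonably associated with the investigational product as assessed by the Sponsor".

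**The concern.** Continued safety is the primary objective, and the cream goes on the whole body every day. Skin reactions judged to be caused by it are the events most relevant to that objective. They are also the only class that the ADR definition removes, and what removes them is the Investigator's own judgement that the drug is responsible.

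Two things are at stake. First, sites are told that these changes are captured somewhere else, but the protocol does not say where, when or on what form. Sites could differ in how they record them. Second, for a serious and unexpected skin reaction, the SUSAR definition and the expedited-reporting sentence give different answers about the same event. The wording should not leave room for that.

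**Working it through.** No arithmetic beyond counting applies, and no event rate is assumed. The check sets the passages side by side.

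**Step 1: is there a skin site evaluation to refer to?**

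The term appears once in the protocol, in the ADR definition. The candidates for what it means are:

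| Candidate | Where | Fits? |
|---|---|---|
| Item in Section 9.3 | Section 9.3 | None of that name. Only tolerability, AEs and physical examinations are listed |
| Application-site tolerability | Sections 9.3 and 11.2 | Plausible, but no scale or form is stated, and the schedule that 11.2 cites for timing has no such row |
| Full skin examination | Section 8.4 | Required at each scheduled study center visit, but not cited by 11.4 and not a schedule row |
| Physical examination | Schedule, Section 11.2 | Includes skin, but marked only at baseline and the final visit |
| BSA | Section 9.2, schedule | Repeated, but scores the extent of blisters and lesions, not drug-related reactions |

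The schedule has 12 procedure rows: consent; inclusion/exclusion; history; physical examination; height, weight and temperature; BSA; pregnancy test; dispensing; collection for accountability; final collection; AEs; concomitant medications. None is named for a skin site evaluation, application-site tolerability or the Section 8.4 skin examination.

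Through month 42, the scheduled study center visits after baseline are visits 2 to 14 (13) plus visit 16 (1), so 13 + 1 = 14. Section 8.4 requires a skin examination at all 14, and the schedule lists it at none of them. AE monitoring is marked at all 14.

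**Step 2: how is one serious, unexpected, SD-101-related skin site reaction classified?**

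| Question | Answer | Source |
|---|---|---|
| AE, recorded in the CRF? | Yes | Sections 11.3, 11.4 |
| Severity and causality graded? | Yes | Section 11.4.1 |
| SAE, reported to the Sponsor within 24 hours? | Yes | Sections 11.4, 11.4.2 |
| SUSAR? | Yes | Section 11.4 |
| IRB/IEC notified under local rules? | Yes | Section 14.1 |
| ADR? | No, by the exception | Section 11.4 |
| Within the ADR-worded expedited sentence? | No, on a literal reading | Section 11.4.2 |

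The last two rows disagree with the SUSAR row.

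**Step 3: how many rules does the exception change?**

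Outside the abbreviation list and the definitions, the protocol uses the term ADR in one operative place, the expedited-reporting sentence. The protocol plans no summary by ADR label. The exception therefore alters one rule.

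**The case against.** The strongest reply is that the safety system works without the ADR label. Every AE is recorded and graded, and every SAE reaches the Sponsor within 24 hours. Expedited reports must follow ICH E2A and the applicable regulations, and the IRB/IEC hears of SAEs and SUSARs. None of these rules has a skin exception. The exception also turns on the Investigator's judgement, whereas the expedited duty turns on the Sponsor's assessment. All of this stands. It limits the consequence, but it does not make the two definitions agree.

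A second reply is that skin site changes may never have been meant to include serious reactions. Section 13 lists severe local and widespread dermatological reactions as intolerable adverse effects, which suggests that the authors thought of them separately. That is a fair reading of intent. Coverage of serious changes is an inference from unqualified wording, not something the text says outright. The text still sets no limit, and one clause would settle it.

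A third reply is that Section 9.3 is not silent, since tolerability monitoring is a plausible meaning of the term. That too stands in part: the fault may be an undefined name for a named assessment, or simply a wrong section number. Tolerability, however, has no schedule row and no stated method, so a site still cannot tell what is meant.

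A reader might infer that skin reactions are excluded from AE or SAE collection, or that no skin check takes place between baseline and the final visit. The documents support neither. The AE and SAE rules apply in full, and Section 8.4 requires repeated skin examinations.

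**Conclusion.** The point holds as a defect of wording with a limited reach. The ADR definition takes out related skin site changes without limit by seriousness. The assessment it relies on is not identified in the protocol or named in the schedule. For a serious, unexpected, related skin reaction, the SUSAR definition and the ADR-worded sentence of Section 11.4.2 conflict on a literal reading.

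Its size is one operative rule, one undefined term and one missing schedule row. How many subjects or events are affected cannot be estimated from the protocol. It is tempting to conclude that related skin reactions have been undercounted or that expedited reports have been missed. That is possible but not shown, because the recording and SAE rules are intact.

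The conclusion rests on two assumptions: that the exception is read as written, and that no document outside the protocol defines the skin site evaluation. It should be corrected, because safety is the primary objective and the correction is cheap.

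**What to change.** - In Section 11.4, delete the exception. At minimum, state that serious skin site changes are not excepted. Either change brings the ADR definition, the SUSAR definition and Section 11.4.2 into agreement for serious events.
- Replace the reference to Section 9.3 with the assessment actually meant: the skin examination in Section 8.4 or application-site tolerability in Section 11.2.
- List that assessment, which the protocol already requires, as a row in the Section 11 schedule.
- State that its findings are recorded as AEs where they meet the AE definition in Section 11.4. Keep the existing provision that routine evolution of the disease may not qualify. In EB, blisters and lesions are the disease, and an unqualified rule would turn expected findings into AEs.
- Reconcile Sections 8.4, 9.3, 11, 11.2, 11.4 and 11.4.2.

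The cost is a short protocol amendment, one schedule row, and a check that skin changes seen before the amendment were recorded as AEs where they qualified. No new visit or procedure is needed.

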11.4.1. Assessment of Causality

Severity

The severity (intensity) of each adverse event will be classified by the Investigator as:

- **Mild** Awareness of sign of symptom, but easily tolerated
- **Moderate** Sign or symptom causes discomfort, but does not interfere with normal activities
- **Severe** Sign or symptom of sufficient intensity to interfere with normal activities

Causality

The likely relationship of each adverse event to the medicinal product will be assessed by the Investigator and reported according to the definitions below:

- **Unrelated** - Event occurred before dosing or
 - Event or intercurrent illness due wholly to factors other than drug treatment.
- **Possibly** - Reasonable temporal relationship with drug treatment.
 - Event could be explained by patient's clinical state or other factors.
- **Probably** - Reasonable temporal relationship with drug treatment.
 - Likely to be known reaction to agent or chemical group, or predicted by known pharmacology.
 - Event cannot easily be explained by patient's clinical state or other factors.
- **Definitely** - Distinct temporal relationship with drug treatment.
 - Known reaction to agent or chemical group, or predicted by known pharmacology.
 - Event cannot be explained by patient's clinical state or other factors.

11.4.2. Adverse Event Reporting

The Investigator shall immediately report any serious adverse event that occurs to the Sponsor. Immediate reporting allows the Sponsor to take the appropriate measures to address potential new risks in a clinical trial. Therefore, the immediate report should be made by the Investigator within a very short period of time and under no circumstances should this exceed 24 hours following knowledge of the serious adverse event.

The Sponsor is required to expedite the reporting to all concerned Investigators / Institutions, to the IRBs, where required, and to the regulatory authorities of all adverse drug reactions (ADRs)

that are serious, unexpected and reasonably associated with the investigational product as assessed by the Sponsor. Such expedited reports should comply with the applicable regulatory requirements and with the ICH Guideline for Clinical Safety Data Management: Definitions and Standards for Expedited Reporting (E2A).

The Sponsor will submit to the regulatory authorities all safety updates and periodic reports, as required by applicable regulatory requirements.

11.5. Concomitant Medications

All concomitant medications and non-drug therapies will be recorded. In addition, concomitant medications and non-drug therapies will be coded for those subjects that experience adverse events.

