7.2. Secondary Objective

The secondary objective is to continue to assess the change in Body Surface Area (BSA) of blisters or lesions.

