8. SELECTION AND WITHDRAWAL OF SUBJECTS

8.1. Subject Numbers

Up to forty-eight EB patients are expected to be enrolled at seven study centers, following completion of their participation in Study SD-003.

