10.4. Duration of Patient Participation

The planned duration of the treatment will vary among subjects and will continue until commercialization or availability of an alternate access approach or study termination by the Sponsor (see [Section 8.4](#) and [Section 13](#) for additional details).

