10.6. Concurrent Therapy

Medications considered necessary for the subject's welfare (intercurrent illness or AEs) may be given at the discretion of the Investigator. The Investigator should consider the necessity of any therapy before prescribing it to the patient. Subjects must be instructed not to take any medications without prior consultation with the Investigator, as feasible. The administration of all such medication / therapy must be recorded in the appropriate section of the eCRF and will be assessed at each visit.

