11.2. Safety Assessments

The safety of SD-101 dermal cream (containing 6% allantoin) applied to the skin, will be assessed by monitoring tolerability at the application sites, adverse events, and physical examinations.

For timing of individual measurements, refer to [Section 11](#) - Study Schedule.

Physical Examination including height, weight, and temperature

Physical examinations will be done by a physician at the final study visit. The physical examination performed at the final visit for SD-003 will be utilized as the baseline assessment for SD-004. The following sites will be examined: head, eyes, ears, nose, throat, neck, chest, lungs, heart, abdomen, skin, and lymph nodes; and the following systems will be assessed: musculoskeletal and neurological. Weight, height, and temperature will be recorded.

Urinalysis

Urine pregnancy test for female subjects of child bearing potential (sensitivity at least 25 mIU/mL) will be performed at visits 4, 6, 8, 10, 12, 14, and at all subsequent study center visits. The urine pregnancy test performed at the final visit for SD-003 will be utilized for entry into SD-004.

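### Does coding concomitant therapies only for subjects with adverse events (Protocol 11.5) distort any result of this study?

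*Protocol*

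**What the plan says.** Section 11.5 consists of two sentences. The first covers collection and has no restriction by subject: "All concomitant medications and non-drug therapies will be recorded". The second adds that "concomitant medications and non-drug therapies will be coded for those subjects that experience adverse events". It does not mention subjects without adverse events, either to include or to exclude them.

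Section 10.6 supports the first sentence: "The administration of all such medication / therapy must be recorded in the appropriate section of the eCRF and will be assessed at each visit". The schedule in section 11 has concomitant medications monitored at every visit, telephone visits included. Section 15.5 lists concomitant medication among the items for the patient file. All three deal with collection, and none mentions coding.

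On analysis, section 12.3 says that results will in general be summarised descriptively and allows further comparison with responses in SD-003. It names no table of concomitant therapy. Safety, the primary objective, "will be assessed by monitoring tolerability at the application sites, adverse events, and physical examinations" (section 11.2). Section 7.2 gives the secondary objective: "The secondary objective is to continue to assess the change in Body Surface Area (BSA) of blisters or lesions".

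**The concern.** Placed straight after a sentence covering all therapies, a coding rule that names one group of subjects reads as a restriction. Whether a subject has an AE is learned after baseline and is a component of the primary safety assessment, so the coded set is selected on outcome. Two features of the study could sharpen this.

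- Section 10.6 allows medication to be given because of AEs, so subjects with AEs probably use more of it than the rest.
- Section 10.4 states that "The planned duration of the treatment will vary among subjects". The longer a subject is followed, the greater the chance of a first AE and so of being coded.

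In a single-arm, open-label extension, co-treatment is ordinary context for reading both the AE profile and the lesion BSA. Section 11.4 adds that changes in the disease may not count as AEs. A subject treated for routine disease activity, with no recorded AE, could therefore have no coded therapy. A drug-class percentage from the coded data would then describe subjects with AEs only. If it were divided by all subjects instead, it would count AE-free users as non-users.

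**Working it through.** There is no stated figure to reproduce. The check has two parts: whether the text restricts coding and any planned result depends on it, and how large the distortion could be if someone built such a table.

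**Text.** Section 11.5 was read against every other place that deals with concomitant therapy: the synopsis and sections 9.3, 10.6, 11 and 15.5. None widens coding. The restrictive reading is the natural one, although the text contains no word such as *only*. Section 12.3 and the objectives in section 7 were then read for any analysis that takes coded therapy as an input. There is none. Causality under section 11.4.1 is judged by the investigator event by event and does not depend on dictionary coding.

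**Size in a hypothetical table.** The only input from the document is the number of subjects: "Up to forty-eight EB patients are expected to be enrolled at seven study centers" (section 8.1), taken as a ceiling. The following are assumptions, because the protocol gives no values:

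- p, the share of subjects with at least one AE
- u1, the share using a given drug class among subjects with an AE
- u0, the share using it among subjects without an AE

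Uncoded subjects = 48 × (1 − p). True use in all subjects = p·u1 + (1 − p)·u0. A coded-only table shows u1, so it overstates use by (1 − p)(u1 − u0). Dividing coded users by all subjects gives p·u1, which understates use by (1 − p)·u0.

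With u1 = 50% and u0 = 20%:

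| p | Uncoded subjects | True use | Coded-only: 50%, too high by | All as denominator: p·u1 |
|---|---|---|---|---|
| 60% | 19.2 | 38.0% | 12.0 points | 30.0% |
| 80% | 9.6 | 44.0% | 6.0 points | 40.0% |
| 90% | 4.8 | 47.0% | 3.0 points | 45.0% |
| 95% | 2.4 | 48.5% | 1.5 points | 47.5% |

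With u1 − u0 = 10 points, the coded-only overstatement is 4, 2, 1 and 0.5 points at the same values of p.

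**Dependence on follow-up.** With a constant first-AE rate r per year (360 days, as in the visit schedule), the share coded by day t is 1 − exp(−r·t/360).

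- r = 0.5: 1 − exp(−0.125) = 11.8% by day 90, and 1 − exp(−1.5) = 77.7% by day 1080.
- r = 1: 1 − exp(−0.25) = 22.1% by day 90, and 1 − exp(−3) = 95.0% by day 1080.

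The day-90 values would matter to a final summary only for subjects who leave that early. The protocol plans no interim summary of medication. For subjects followed to month 36, the day-1080 values apply.

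**The case for a change.** The best argument for a change is that this is no mere silence. The protocol states a coding rule and gives it a scope selected on outcome, so an analysis plan that coded everyone would go beyond what the protocol describes. The collection effort has already been spent, at most about 48 subjects are involved, and one sentence would remove the selection at almost no cost. Describing co-treatment in all treated subjects is also normal practice in an uncontrolled study.

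Much of this stands. The reading of section 11.5 is right, the selection is real, and wider wording would be cheap. What does not stand is the step from there to a harmed result. The rule commits the sponsor to code one group and does not forbid coding the others, so an analysis plan or data management plan could cover everyone without contradicting it. The information is not lost either, because the entries are in the eCRF for every subject. The harm would arise only if an analyst produced a table that the protocol does not plan and also used the wrong base for it. An analyst who wanted use by drug class in all treated subjects would see that the AE-free subjects were uncoded and have them coded first.

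**Conclusion.** The observation is correct, but no change to the plan follows, because changing it would gain nothing for any result the protocol names. The primary safety objective rests on AEs, application-site tolerability and physical examination. The secondary objective rests on BSA. Neither uses coded therapy, and investigator causality assessment does not either.

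The size of the effect in a hypothetical drug-class table is unknown, since p, u1, u0 and the AE rate are all assumed. The larger figure, 12 points, needs both a 40% AE-free share and a 30-point difference in use. Section 11.3 collects AEs from consent through the final visit. Section 11.4 counts new illness and worsening of pre-existing conditions, and one mild, unrelated event is enough for a subject to be coded. Visits are scheduled to month 36 and beyond. These features make a high share with AEs plausible, though they do not prove it. At 90% to 95% the overstatement is 0.5 to 3 points, from about 2 to 5 uncoded subjects out of 48.

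One caution remains for whoever reports the study: a summary made from the coded records alone should be labelled as describing subjects with AEs, or the remaining entries should be coded first.
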